## 2.8 Pharmacokinetic endpoints

There are no pharmacokinetic (PK) endpoints defined for this study.

## 2.9 PD and PK/PD analyses

There are no pharmacodynamic (PD) or PK/PD analyses planned for this study.

## 2.10 Patient-reported outcomes

PRO measures included in this study are the NeuroQOL™ and the PDDS. Analysis of these PRO measures supports secondary objectives.

The NeuroQOL™ is a measurement system that evaluates and monitors the physical, mental, and social effects experienced by adults and children living with neurological conditions ([://healthmeasures.net/explore-measurement-systems/neuro-qol](http://healthmeasures.net/explore-measurement-systems/neuro-qol); [Miller et al., 2016](#)). The following domains will be measured:

- Physical Health: Fatigue, Sleep disturbance, Lower Extremity function (mobility), Upper Extremity Function (Fine motor, ADL), Urinary/Bladder Function and Bowel Function (custom 14-item short form)
- Mental Health: Anxiety, Depression, Cognitive Function, Communication, Positive Affect and Well-Being
- Social Health: Ability to Participate in Social Role and Activities

The PDDS is a standardized rating scale developed by [Hohol et al. 1995](#), which is a self-assessment scale of functional disability in multiple sclerosis patients primarily based on ambulation. The questionnaire contains 1 question which is scored ranging from 0 (normal) to 8 (bedridden) ([://nationalmssociety.org/For-Professionals/Researchers/Resourcesfor-Researchers/Clinical-Study-Measures/Disease-Steps-\(DS\)](http://nationalmssociety.org/For-Professionals/Researchers/Resourcesfor-Researchers/Clinical-Study-Measures/Disease-Steps-(DS))). A score of 0 to 2 indicates mild disability; a score of 3 to 5 indicates moderate disability; a score of 6 to 8 indicates severe disability ([Hohol et al., 1995](#)).

Values and changes from baseline in NeuroQOL™ short form domain T-scores, and the PDDS score, will be summarized by Cohort and time point with descriptive statistics using the FAS or HCAS, as appropriate. In addition, changes from Month 6 to post-Month 6 time points will be summarized in a similar fashion.

Details on the derivation of total raw scores and the conversion of those total raw scores to T-scores for the NeuroQOL™ short form domains are provided in the TFL Shells document; they are based on NeuroQOL™ Scoring Manual version 5.0 dated September 2022. Note that total raw scores and T-scores will not be derived for the urinary and bowel custom 14-item short form. In addition, only the total raw score for the communication short form domain will be summarized; no T-score is determined since this short form domain is comprised of uncalibrated items.

[REDACTED]

[REDACTED]

- [REDACTED]
- [REDACTED]
- [REDACTED]
- [REDACTED]
- [REDACTED]
- [REDACTED]

[REDACTED]

[REDACTED]

[REDACTED]

[REDACTED]

[REDACTED]

- [REDACTED]
- [REDACTED]

## 2.13 Interim analysis

There will be one interim analysis after the last participant completes his/her Month 18 (primary analysis time point) visit.

The presentation of tables, listings, and figures will include data up to participants' date of Month 18 visit (inclusive). All available data for participants discontinuing the study prior to Month 18 will be included in the interim analysis.

This interim analysis will be the primary analysis. There will be neither hypothesis testing nor estimation at Month 30. Therefore, no statistical adjustment will be made at Month 18.

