¹⁶ Administration of ofatumumab (at study site or at home) should occur after the study visit assessments are performed, if on the same day of the study visit

¹⁷ Study drug self-injection (at-home or on-site) will be performed **monthly**, beginning at Week 4, by all ofatumumab participants

¹⁸ MRI assessment must be completed within +/-7 days of the visit

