8.3.6 Magnetic Resonance Imaging (MRI)

All participants will undergo MRI scanning of the brain, within +/- 7 days of the visit, according to the assessment schedule in Table 8.1.

MRI scans will be read by the central MRI reading center. Prior to the start of the study, the MRI technician from each study site will receive an MRI Manual, outlining the minimum criteria needed for MRI capabilities, technical implementation, image quality requirements and MRI administrative procedures.

The site will be asked to program the MRI scanner that is designated for evaluation of the study participants. Site will be asked to perform and submit a dummy scan (so called “dummy or dry run”) to the central MRI reading center to assess the image quality and to evaluate the compatibility of the electronic data carrier. Once the dummy run has been accepted, all the parameter settings for the study specific MRI sequences must remain unchanged for the duration of the study. Finally, if the site is already pre-approved for performing conventional MRI scan sequences by the imaging vendor, the dummy or dry run may be skipped.

Each MRI scan performed for the study needs to be previewed by a local neuroradiologist. During the study, the quality of each scan performed will be assessed by the central MRI reading center. The MRI scan should be sent to the central MRI reading center upon completion of each individual scan. As soon as the scan is received by the central MRI reading center, it will be evaluated for quality, completeness and adherence to the protocol. Confirmation of MRI quality or a description of the quality problems, if detected, will be communicated to the site. If a scan is incomplete or incorrectly performed, the study center will be asked to repeat it as soon as possible. After completion of the quality check, all scans will be analyzed according to the MRI protocol.

Restrictions to MRI schedule

To avoid interferences caused by steroids (in regard to Gd⁺-enhancing lesions) for the treatment of MS relapse and diagnostic challenges with concomitant participant migraines, the following restrictions apply for this study:

- In case of relapse, if an MRI has been scheduled within 30 days of the initiation of steroid treatment, MRI (with Gd⁺ enhancement) should be performed **before** steroid treatment is initiated.

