## 2 Statistical methods

### 2.1 Data analysis general information

The statistical analysis outlined in this SAP will be performed by United BioSource LLC (UBC), a Novartis-designated Contract Research Organization (CRO), using SAS® version 9.4 or higher.

The primary analysis will be based on Month 18 data, i.e., all data up to and including Month 18. This analysis will be performed after all participants have completed their Month 18 visit, discontinued study treatment prior to Month 18 (ofatumumab-treated participants) or discontinued the study prior to Month 18 (healthy control participants) (see [Section 2.1.1](#) and [Section 2.13](#) for additional details). The final analysis will include all data through Month 30.

For continuous variables, descriptive statistics will include number of participants (n) with available data, mean, standard deviation, minimum, maximum, median and 25th and 75th percentiles. For categorical variables, frequency counts and percentages will be reported. Where appropriate, 2-sided 95% confidence intervals (CIs) for point estimates of the mean or proportion will be provided.

In general, data summaries will be presented for ofatumumab-treated participants in the relevant analysis set. In instances where data are collected for both ofatumumab-treated participants and healthy control participants, data summaries will be presented **by Cohort** (ofatumumab-treated participants or healthy control participants) and on all participants in the respective analysis set.

All data (collected or derived) will be listed appropriately.

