## Month 18 interim analysis data cut-off

As noted in [Section 2.1](#), the primary analysis will be based on Month 18 data (i.e., all data up to and including Month 18) and performed after all participants have completed their Month 18 visit, discontinued study treatment prior to Month 18 (ofatumumab-treated participants) or discontinued the study prior to Month 18 (healthy control participants). The data cut-off for the Month 18 interim analysis is defined for different participant scenarios in [Table 2](#). Note that visits are assumed to be nominal visits.

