**Table 2 Month 18 interim analysis data cut-off for different participant scenarios**

Participant scenario	Cut-off	Participant data included in Month 18 interim analysis (primary analysis)
Completed Month 18 visit	Date of Month 18 visit + 7 days (inclusive)	All available data up to the date of the Month 18 visit + 7 days (inclusive)*
Did not complete Month 18 visit		
Discontinued study prior to Month 18 visit	None	All available data
Did not discontinue study prior to Month 18 visit	Date of next scheduled visit after Month 18 (exclusive)	All available data up to the date of the next scheduled visit (including home visit) after Month 18 (exclusive).** If the next scheduled visit after Month 18 has not been completed, all available data is used.

\* Including data such as adverse events, medications, non-drug therapies/procedures, protocol deviations and relapses that started prior to or on the date of the Month 18 visit + 7 days.

\*\* Including data such as adverse events, medications, non-drug therapies/procedures, protocol deviations and relapses that started prior to the date of the next scheduled visit (including home visit) after Month 18.

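### SAP 2.13 ends the Month 18 primary-analysis data at the visit date, while SAP 2.1.1/Table 2 ends them 7 days later; applied literally, 2.13 would drop compliant late MRI scans

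*SAP*

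**What the plan says.** Two parts of the current SAP fix the data cut-off for one analysis.

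- **SAP 2.13 (Interim analysis):** the outputs present data only as far as each participant's "date of Month 18 visit (inclusive". The same section states that this interim analysis is the primary analysis. The sentence also stands in protocol 12.7.
- **SAP 2.1.1:** "The data cut-off for the Month 18 interim analysis is defined for different participant scenarios in" Table 2. For a participant who completed the Month 18 visit, Table 2 includes "All available data up to the date of the Month 18 visit + 7 days (inclusive". Its footnote applies the same limit to the start dates of relapses, adverse events, medications, procedures and protocol deviations.
- **SAP 2.1:** "The primary analysis will be based on Month 18 data, i.e., all data up to and including Month 18". It then sends the reader to both 2.1.1 and 2.13 without saying which prevails.

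The MRI timing comes from the protocol. Table 8-1, footnote 18, says "MRI assessment must be completed within +/-7 days of the visit", and protocol 8.3.6 says the same: "All participants will undergo MRI scanning of the brain, within +/- 7 days of the visit".

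SAP Table 6 runs the Month 18 MRI window from day 451 to the cut-off day and takes that day from 2.1.1. Later scans fall into the Month 30 window. Under SAP 2.2 and 2.5.3, a participant who completed the Month 18 visit but missed the Month 18 MRI leaves mFAS unless disease activity was shown. Under SAP 2.5.6 and 5.1.3.3, the non-response analysis sets such a participant's NEDA-3 to No.

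**The concern.** The two rules differ by exactly the 7 days in which a protocol-compliant Month 18 scan may still be done. A scan on the third day after the visit is a Month 18 scan under Tables 2 and 6, but 2.13 bars it from the outputs. Relapses and adverse events that start in those days are treated inconsistently in the same way, as are the other Month 18 MRI outputs, including those of the healthy controls.

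The primary endpoint is the most exposed, because the mFAS rule depends on outcome. A participant whose activity is already on record stays in as a failure. One with no activity shown, and no other scan in the window, leaves. Losing late scans could therefore lower the NEDA-3 proportion as well as widen its interval. The trial is open-label, so the choice of rule should not be left to programming.

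**Working it through.** **1. The plan's own figures.** SAP Section 3.1 gives 100 evaluable participants, half-widths of 7.8% and 7.0% at NEDA-3 rates of 80% and 85%, 15% drop-out and 118 enrolled.

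- 1.96 × √(0.80 × 0.20 / 100) = 7.84%
- 1.96 × √(0.85 × 0.15 / 100) = 7.00%
- 100 / 0.85 = 117.6, rounded up to 118

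All reproduce. They use the normal approximation. The planned Clopper-Pearson interval at n = 100 has half-widths of 8.3% and 7.4%. The normal approximation is kept below only so that results compare with the plan's figures.

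**2. The cut-offs side by side.** The permitted MRI days run from −7 to +7, which is 15 days.

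| Rule | Last day included | Permitted MRI days inside | Outside |
|---|---|---|---|
| SAP 2.13 | visit + 0 | 8 | 7 |
| SAP 2.1.1/Table 2 | visit + 7 | 15 | 0 |

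These are counts of days, not of scans.

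**3. What would follow if 2.13 were applied over Tables 2 and 6.** Inputs:

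- 100 otherwise evaluable participants with a NEDA-3 rate of 80%, both from the plan.
- f, the share of Month 18 scans dated after the visit. This is an assumption, because the documents do not give it.
- g, the share of the 20 failures already shown without the Month 18 scan. This is taken at its extremes, 1 and 0.
- Late scanning is unrelated to outcome, and no second scan falls in the window. Both are assumptions.

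Formulas:

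- successes kept = 80(1 − f)
- failures kept = 20g + 20(1 − g)(1 − f)
- mFAS = successes kept + failures kept
- observed rate = successes kept / mFAS
- half-width = 1.96 × √(rate × (1 − rate) / mFAS)
- non-response rate over the same 100 = 80(1 − f) / 100

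For f = 10% and g = 1, mFAS = 72 + 20 = 92 and the rate is 72/92 = 78.3%. For g = 0, mFAS = 72 + 18 = 90 and the rate is 80%.

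| f (assumed) | mFAS | Observed NEDA-3 | Half-width | Non-response analysis |
|---|---|---|---|---|
| 0 | 100 | 80% | 7.8% | 80% |
| 10% | 90-92 | 78.3-80% | 8.3-8.4% | 72% |
| 25% | 75-80 | 75.0-80% | 9.1-9.5% | 60% |
| 50% | 50-60 | 66.7-80% | 11.1-11.9% | 40% |

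In each range of the observed rate, the lower end is g = 1 (all failures already known) and 80% is g = 0 (all failures visible only on the Month 18 scan). The last column is over the same 100 participants. The full analysis set would also hold the drop-outs.

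**4. If Table 2 is followed.** Every scan in the permitted window is kept, f has no effect, and the planned 100 stands as far as this point is concerned.

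**The case against.** The strongest reply is that the SAP already works from Table 2. Section 2.1.1 presents Table 2 as the definition, and one of its columns is expressly about data in the primary analysis. The visit windows in Tables 3 to 6, the split between treatment phase and extension, and the treatment-phase duration all use the 2.1.1 cut-off. No legible derivation relies on the 2.13 sentence, which looks like protocol 12.7 carried over. The document history for SAP Amendment 1 records a deliberate move to 7 days and names only Section 2.1.1, which suggests that 2.13 was simply not updated. On that reading a day +3 scan is a Month 18 scan, it was not missed, and nobody leaves mFAS.

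This largely stands. It makes Table 2 the likely intent and means that loss occurs only if 2.13 is put above Tables 2 and 6. It does not remove the conflict: both statements are current text about the same outputs, and 2.1 refers to both without ranking them.

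Three stronger readings are tempting, and the documents support none of them:

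- **That 2.13 governs the outputs, so scans will be lost.** The SAP gives 2.13 no such priority.
- **That 7/15 = 47% of scans would go, leaving 53 of 100.** This assumes scan dates spread evenly over the window, for which there is no information. It also removes participants whose activity was already shown, although they stay in mFAS. Even at f = 7/15 the range is about 53 (100 × 8/15) to 63 (20 + 80 × 8/15).
- **That the 7 days were added because of the MRI window.** The numbers match and the inference is plausible, but the SAP does not give this reason.

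**Conclusion.** The contradiction is real and concerns the data that enter the primary analysis. Its effect is conditional. Under Table 2 there is none. Under 2.13 applied literally, compliant scans dated 1 to 7 days after the visit drop out, as do relapses and adverse events that start in those days.

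The size then depends on an unknown share of late scans, so the scenario figures illustrate and do not predict. The downward bias in the mFAS proportion is possible, not certain: it vanishes if every failure is visible only on the Month 18 scan. The non-response analysis is the more sensitive. In the scenarios, 10% late scans would cost it 8 points, about the planned half-width. All of this concerns participants who completed the Month 18 visit, since Table 2 has separate rules for the others.

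**What to change.** Replace the cut-off sentence in SAP 2.13 with a reference, for example: *Outputs for the Month 18 analysis include data up to the Month 18 cut-off defined in Section 2.1.1, Table 2.* This also brings in Table 2's rule for participants who missed the Month 18 visit but stayed in the study, whom 2.13 does not mention.

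List the departure from protocol 12.7 in SAP Section 4. No legible bullet there covers it, but some bullets are redacted, so first check whether one already does.

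The cost is one sentence and at most one bullet, before the Month 18 outputs are produced. No derivation in Tables 3 to 6 needs to change.

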## 3 Sample size calculation

### 3.1 Primary endpoint(s)

Ofatumumab sample size calculations were based on the proportion of participants with NEDA-3 in Months 6 to 18.

A sample size of 100 participants will provide a 7.8% precision (half-width of 95% CI), or a 7.0% precision corresponding to estimated proportions of 80% and 85% of participants achieving NEDA-3. Adjusting for a 15% drop out rate, 118 participants will be enrolled in the study.

### 3.2 Secondary endpoint(s)

A sample size of 50 age- and sex-matched healthy controls with no diagnosis of neurologic disease will be enrolled.

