4.1 Rationale for study design

This study is an open-label, multi-center, prospective eighteen-month study in a minimum of 118 MS patients with early RRMS (defined as within 6 months of diagnosis of clinically definite RRMS) and who are DMT treatment naïve. RMS patients will be benchmarked against age- and sex-matched healthy controls (n=50) for select secondary [REDACTED]. The concept herein will expand on previous ofatumumab studies and provide important clinical and safety data in an earlier RRMS population than studied in ASCLEPIOS I and II. Further, this study will investigate multiple secondary [REDACTED] (over the course of up to 30 months; all patients are in trial for 18 months, but the optional extension period extends to 30 months) to build the data sets on early use of ofatumumab using MRI metrics, patient reported outcomes (PRO), biomarker and digital monitoring technologies. Finally, the study will compare select endpoints vs age- and sex-matched HC patients to provide first evidence of safety and disease stabilization measured by MRI/[REDACTED] vs non-MS patients.

Due to the limited time from diagnosis and lack of experience with B cell depleting therapies that this population will have, an open-label, multi-center design was selected to facilitate recruitment. Further, the clinical trial space is very active with numerous therapies under development and therefore careful consideration was taken regarding impact on the patient when designing monitoring outcomes. The design limited the number of clinic visits and MRIs to minimum acceptable levels and focused on using “at home” digital technology for monitoring when available.

Finally, the use of a HC group for comparison is novel in the clinical trial program for ofatumumab. In the Phase 2 APOLITOS trial, a Japanese/Russian population was studied to evaluate the efficacy and safety of ofatumumab versus placebo in RMS patients. Although this study included RMS placebo-treated patients, no study has compared ofatumumab treated patients to non-MS HCs. The HC comparator data can provide important information on safety outcomes (e.g., infections) and the ability of ofatumumab to normalize CNS pathology as measured by MRI and [REDACTED] of disease.

Rationale of chosen endpoints:

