5.1 Inclusion criteria

Participants eligible for inclusion in this study must meet **all** of the following criteria:

1. Signed informed consent must be obtained prior to participation in the study
2. Age 18-35 years

Patients in the healthy control arm eligible for inclusion must fulfill the following criteria:

3. Able to obtain MRI (HC with abnormal MRI at Screening will be excluded) and use wearable device
4. Able to provide blood sample (no CSF will be collected in HC)

Patients in the ofatumumab-treated arm eligible for inclusion must fulfill the following criteria:

5. Diagnosis of RRMS per McDonald Criteria (2010/2017)
6. Within 6 months of diagnosis of clinically definite MS (CDMS)
7. EDSS 0-3.0 (Inclusive) at both screening and baseline
8. Treatment-naïve to MS DMT
9. Able to obtain MRI and attend study visits at sites
10. Able to use wearable device
11. Able to provide blood sample (and CSF for sub-group n=15)
12. If a participant is receiving dalfampridine (Ampyra[®]/Fampyra[®]) concomitantly with study treatment, the participant should have been on a stable dose at least 30 days prior to first study drug administration and remain on that dose throughout the study wherever possible

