5.2 Exclusion criteria

Participants in the healthy control arm meeting any of the following criteria are not eligible for inclusion in this study:

1. Confounding medical condition as determined by the investigator

Participants in the ofatumumab-treated arm meeting any of the following criteria are not eligible for inclusion in this study:

2. Diseases other than multiple sclerosis responsible for the clinical or MRI presentation
3. Patients with neuromyelitis optica, Radiologic/Clinically Isolated Syndrome, Secondary Progressive or Primary Progressive MS diagnosis
4. Use of experimental or investigational drugs for MS. Use of other investigational drugs within 5 half-lives of enrollment/initiation of study treatment (select as appropriate) within 30 days (e.g. small molecules) / or until the expected pharmacodynamic effect has returned to baseline (e.g. biologics), whichever is longer; or longer if required by local regulations
5. Previous use of Disease Modifying Therapy (DMT) or chemotherapeutic medications for MS
6. Relapse between screening and Baseline visits
7. Known sensitivity to gadolinium; patients with chronic, severe kidney disease (GFR < 30 mL/min/1.73m²) or acute kidney injury (contraindicated with use of gadolinium)
8. Known history of hypersensitivity to any of the study treatments or its excipients or to drugs of similar chemical classes
9. CNS anomalies that are better accounted for by another disease process (e.g. traumatic brain injury) or MRI anomalies causing clinically apparent impairments in social, occupational, or generalized areas of functioning, due to the direct physiologic effects of substances (recreational drug abuse, toxic exposure, etc) or a medical condition

10. Known active malignancies
11. Pregnant or nursing (lactating) women, where pregnancy is defined as the state of a female after conception and until the termination of gestation, confirmed by a positive hCG laboratory test
12. Females of childbearing potential (all women physiologically capable of becoming pregnant) **unless** they are using effective contraception while receiving ofatumumab, and for 6 months after the last treatment of ofatumumab

Effective contraception methods include:

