### 1.1 Study design

This study is an open-label, multi-center, prospective eighteen-month study in a minimum of 118 multiple sclerosis (MS) patients with early relapsing-remitting MS (RRMS) (defined as within 6 months of diagnosis of clinically definite RRMS) and who are disease modifying therapy (DMT) treatment naïve. RRMS patients will be benchmarked against age- and sex-matched healthy controls (n=50) for select secondary [REDACTED] outcomes.

The study consists of 3 main periods/phases as outlined below. In addition, a safety follow-up period applies to participants who meet specific criteria as described below.

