**Table 1 Study objectives and endpoints**

Objective(s)	Endpoint(s)

Primary Objective(s)
 
 
The primary objective is to explore the impact of ofatumumab on the ability to achieve No Evidence of Disease Activity (NEDA-3) status in treatment-naïve, very early RRMS participants over an 18 month, open-label study period after a re-baseline of MRI at 6 months
 
	
Endpoint(s) for primary objective(s)
 
 
NEDA-3 (relapse-free, 3-month clinical disability progression-free, MRI activity-free) in Months 6 to 18 (yes/no)
 

Secondary Objective(s)
 
 
Evaluate the effect of ofatumumab on various clinical (NEDA, disability, relapse) metrics at 18 months
 
Evaluate the effect of ofatumumab on conventional MRI metrics, with MRIs at Baseline and Months 6, 12, 18, 30 (T1 gadolinium (Gd) @ Baseline, Month 6, 18 and T1/T2 @ every timepoint)
 
Evaluate the effect of ofatumumab on patient reported outcomes (PROs) (Quality of Life in Neurological Disorders [NeuroQOLTM], Patient Determined Disease Steps [PDDS])
 
Evaluate the effect of ofatumumab vs healthy controls on 1) whole brain and regional atrophy measured at Month 18/30 after re-baseline at 6 months; and 2) regional atrophy measured 18/30 months from Baseline
 
Evaluate the safety and tolerability of ofatumumab
 
	
Endpoint(s) for secondary objective(s)
 
 
Number of confirmed relapses in Months 6 to 18
 
3-month disability worsening-free in Months 6 to 18 (yes/no)
 
NEDA clinical in Months 6 to 18 (yes/no)
 
NEDA radiological in Months 6 to 18 (yes/no)
 
Change from baseline in conventional MRI metrics (Gd+ lesion number, new Gd+ lesion number, Gd+ lesion volume, T2 lesion number (Baseline), new/enlarging T2 lesion number (post-Baseline), T2 lesion volume, new/enlarging T2 lesion volume, new unenhancing T1 lesion number, T1 unenhancing lesion volume)
 
Change from baseline in PROs (NeuroQOLTM, PDDS) (also obtained in healthy controls)
 
Brain volume assessment (whole brain and regional) (also obtained in healthy controls)
 
Adverse events, laboratory data, physical examination, and vital signs (also obtained in healthy controls)
 

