## 2.2 Analysis sets

The Full Analysis Set (FAS) will include all enrolled participants that received any study drug.

The Safety Analysis Set (SAF) will be the same as the FAS.

The Healthy Control Analysis Set (HCAS) will include all enrolled healthy control participants. This analysis set will be used in the analysis of data collected from healthy control participants.

The modified FAS (mFAS) will include all participants in the FAS except for those who discontinued treatment prematurely prior to Month 18 for reasons other than lack of efficacy or death, or those who completed their Month 18 visit but missed relapse/EDSS/MRI (Gd+ or

new/enlarging T2 lesions) at Month 6, 12 or 18, unless they showed disease activity (i.e., MRI activity after Month 6 through 18 or relapse/3-month clinical disability progression between Months 6 and 18). The mFAS will be used for NEDA-3, NEDA clinical and NEDA radiological efficacy analyses.

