## 2.6.2 Statistical hypothesis, model, and method of analysis

Values, changes from baseline and percent changes from baseline (brain volume parameters only) in the following endpoints will be summarized by Cohort and time point with descriptive statistics using the FAS or HCAS, as appropriate:

- Conventional MRI metrics including Gd+ lesion number, Gd+ lesion volume, T2 lesion volume and T1 unenhancing lesion volume
- Brain volume parameters (whole brain and regional)

In addition, changes and percent changes (for applicable endpoints) from Month 6 re-baseline to post-Month 6 time points will be summarized in a similar fashion.

Percent change from Month 6 re-baseline to post-Month 6 time points in brain volume parameters will be calculated via the following steps:

1. Calculate normalized brain volume (NBV) at post-baseline time points as follows (note that NBV at baseline and percentage brain volume change [PBVC] at post-baseline time points are provided by the MRI vendor):  
NBV at post-baseline time point = [(PBVC at post-baseline time point/100) x NBV at baseline] + (NBV at baseline)
2. Calculate the percent change from Month 6 re-baseline to post-Month 6 time points using the NBVs at Month 6 re-baseline and Months 12, 18 and 30 from Step 1 according to the formula provided in [Section 2.1.1](#).

Values of the following endpoints will be summarized by Cohort and time point (baseline or post-baseline, as appropriate) with descriptive statistics using the FAS or HCAS, as appropriate:

- Conventional MRI metrics including new Gd+ lesion number, T2 lesion number, new/enlarging T2 lesion number, new unenhancing T1 lesion number and new/enlarging T2 lesion volume

The annualized new/enlarging T2 lesion rate will be calculated using a participant-based approach and a cohort-based approach as follows:

- Participant-based approach: [(number of new/enlarging T2 lesions in Months 6 to 18 for a given participant) / (number of days in Months 6 to 18 for a given participant)] × 365.25
- Cohort-based approach: [(total number of new/enlarging T2 lesions in Months 6 to 18 for all participants within a cohort) / (total number of days in Months 6 to 18 for all participants within a cohort)] × 365.25

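### The healthy controls are called age- and sex-matched, but no visible text shows how, and the cohort benchmarks adjust for neither factor

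*SAP*

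**What the plan says.** **Design and sizing text.** SAP 3.2 states "A sample size of 50 age- and sex-matched healthy controls with no diagnosis of neurologic disease will be enrolled". SAP 1.1 says "RRMS patients will be benchmarked against age- and sex-matched healthy controls (n=50) for select secondary" and further outcomes that are redacted. Protocol 4.1 says "the study will compare select endpoints vs age- and sex-matched HC patients". Protocol 3 and 12.8.2 use the same description. The clause about having no neurologic diagnosis appears only in the two sizing sections (Protocol 12.8.2, SAP 3.2).

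**Objective.** SAP Table 1 reads "Evaluate the effect of ofatumumab vs healthy controls on 1) whole brain and regional atrophy measured at Month 18/30 after re-baseline at 6 months". It names healthy controls only and does not mention matching.

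**Eligibility.** Both cohorts must consent and be 18-35 years old. Controls must also be "Able to obtain MRI (HC with abnormal MRI at Screening will be excluded) and use wearable device" and able to give blood. The one exclusion specific to controls is "Confounding medical condition as determined by the investigator". Sex is not mentioned.

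**Analysis.** SAP 2.2 says "The Healthy Control Analysis Set (HCAS) will include all enrolled healthy control participants". Under SAP 2.6.2, MRI and brain-volume results "will be summarized by Cohort and time point with descriptive statistics using the FAS or HCAS, as appropriate", and SAP 2.10 treats NeuroQOL and PDDS in the same way. SAP 2.3.2 tabulates age and sex by cohort. SAP 2.2.1 plans no subgroup analysis, and SAP 2.6.5 and 2.6.6 plan no sensitivity or supplementary analyses of secondary endpoints.

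**The concern.** The controls are there to support a statement about normalisation of brain structure and function (Protocol 1.2). Allocation is not randomised: patients are treated and volunteers are not. Matching is therefore the only visible protection against age and sex differences between the two columns, and the analysis adds none.

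If matching was loose or absent, a difference in brain-volume change or patient-reported change could partly reflect who was recruited, or a real difference could be hidden. A report that repeats the design wording would still describe the columns as matched. The demographic table would show an imbalance but would not remove its effect on the endpoints.

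**Working it through.** **1. The plan's own figures.** No effect size, SD, precision target, matching ratio or dropout rate is given for the 50 controls, so that number cannot be reproduced. The neighbouring ofatumumab figures (SAP 3.1) can be:
- 1.96 × √(0.80 × 0.20/100) = 7.84%, stated as 7.8%.
- 1.96 × √(0.85 × 0.15/100) = 7.00%, stated as 7.0%.
- 100/0.85 = 117.6, rounded up to 118, as stated.

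**2. Where a matching rule could appear.**
- Protocol 5.1 and 5.2: a common age range, nothing on sex.
- Protocol 6.4.1 and 6.4.2 (numbering and assignment): no matching step. Protocol 6.3.2 says there is no randomisation.
- SAP 2.2 and 5.5: no matched set or pairs.
- SAP 2.6.2 and 2.10: no age or sex term, strata or pairing.

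The ratio is 118/50 = 2.36. One-to-one matching would use 50 patients and two-to-one would use 100. Individual matching at a fixed ratio therefore cannot use everyone, and some frequency-matching rule would be needed. None is visible.

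**3. Chance imbalance in sex without enforced matching.** Inputs: 118 and 50 from the plan; the share of women, p, is assumed equal in both sources.

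SE of the difference = √[p(1−p)(1/118 + 1/50)], with 1/118 + 1/50 = 0.02847.

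| Assumed p | SE (points) | Chance of a gap above 10 points (normal approximation) |
|---|---|---|
| 0.60 | 8.3 | 23% |
| 0.70 | 7.7 | 20% |
| 0.80 | 6.7 | 14% |

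Exact binomial enumeration for a gap of at least 10 points gives 24%, 23%, 20% and 17% at p = 0.50, 0.60, 0.70 and 0.75. A gap of at least 15 points has a chance of 8% down to 4% over the same range. Different recruitment sources for patients and volunteers could make the gap larger.

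**4. What a gap could do to a mean.** Bias in SD units = gap in the share of women × sex effect in SD. The documents give neither input, so both are assumed: gaps of 0.10 to 0.30 and sex effects of 0.2 to 0.8 SD.
- Smallest: 0.10 × 0.2 = 0.02 SD.
- Middle: 0.20 × 0.5 = 0.10 SD.
- Largest: 0.30 × 0.8 = 0.24 SD.

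For comparison, the 95% half-width of a cohort difference is 1.96 × √0.02847 = 0.33 SD. Over this range the bias stays below the sampling uncertainty, but at the top it is a large part of it (0.24/0.33 = 73%).

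**The case against.** **Silence is not absence.** The protocol says repeatedly that the controls are matched. The mechanics may sit in redacted text, in the interactive response system, which takes identifying information at registration (Protocol 6.4.1), or in a manual. This stands. A reader might infer that the controls are not matched at all, but the documents do not support that. They show only that no procedure is visible and that the analysis does not use one.

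**Part of the problem is already contained.** Age is limited to 18-35 in both cohorts. Brain volume is analysed as within-person percent change, and the patient-reported outcomes include change from baseline, so stable differences in level largely cancel. This also stands, but it does not cover rates of change that differ by sex, and it sets no limit on the sex mix.

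**The comparison is descriptive.** SAP 5.4.2 plans no test for secondary objectives. That lowers the stakes. It does not make two unadjusted columns comparable.

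**Neurologic disease among the controls.** A reader might infer that the benchmark could be contaminated, because no control criterion names neurologic disease and the control analysis set keeps every enrolled control. The documents largely answer this. An abnormal screening MRI excludes a control, as does a confounding medical condition. Medical history and a physical examination are taken at screening (Protocol Table 8-1), and the protocol glossary defines a healthy volunteer as having no known significant health problem. Removing controls from the analysis set for an undefined neurologic history would filter one cohort only and could make the benchmark artificially healthy. What remains is a wording mismatch.

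**Conclusion.** The point holds as a gap between description and analysis. Matching is asserted in five sections, no visible text puts it into operation, and the non-randomised benchmarks in SAP 2.6.2 and 2.10 are unadjusted. Sex is the main exposure, because age is bounded by eligibility.

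The 14-23% chance of a gap above 10 points assumes 60-80% women in both sources and no enforced matching. The step from that gap to an endpoint rests on sex effects that the documents do not supply, so 0.02-0.24 SD is an illustration and not an estimate.

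Two stronger readings should not be drawn. The stated objective does not promise matched controls; it says healthy controls. The primary NEDA-3 result is also not at risk, because it is a proportion in treated patients only. This is an inexpensive improvement to secondary comparisons and changes no stated number.

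**What to change.** 1. **SAP 2.6.2 and 2.10.** For percent change in brain volume (from baseline and from Month 6) and for NeuroQOL and PDDS change, keep the raw by-cohort summaries. Beside them, add a cohort difference with a 95% confidence interval from a linear model with terms for cohort, sex and continuous age. No test is needed. A model is preferable to sex by age-band cells: if 20-40% of the 50 controls are men, there are 10-20 men, or about 5-10 in each of two age bands.
2. **SAP 1.1 and 3.2.** Either cite the matching procedure (factors, ratio, tolerance and where it is documented) or describe the controls as aged 18-35, with comparisons adjusted for age and sex.
3. **At most,** reconcile the control criteria in Protocol 5.2 with the neurologic-diagnosis clause in Protocol 12.8.2. The control analysis set need not change.

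**Cost.** Age and sex are already collected in both cohorts, so no participant, visit or procedure is added. The price is a few table columns and slightly wider uncertainty for the controls.
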